For WP2, data on volume will be linked to responses to our national survey of governance leads in NHS and independent hospitals. For WP3 we will provide information on potential clusters of NHS and independent hospitals to inform case study selection. For WP4 and WP5 we will provide information on volume, case-mix and coding practice for areas of overlap across the NHS and independent sector. This list is likely to include procedures in specialties such as general surgery, urology, trauma and orthopaedics, ENT, ophthalmology and cardiology.

Case-mix

Using patient level data from Hospital Episode Statistics we will compare the case-mix of patients. This will include patients whose treatment is NHS funded regardless of where the treatment occurs, and privately funded care in NHS private patient units. We will compare patient socio-demographic characteristics (gender, age, ethnicity, deprivation of the patient's local area) and medical characteristics (length of stay, presence and count of comorbidities). These case-mix variables will be summarised by provider type (NHS hospital, NHS private patient unit), funding source, geographical region and over time.

For our analysis of case-mix we will estimate a prediction model for patients in quadrants A, B and C using mortality as the outcome for each patient. We will compare expected vs actual outcomes for patients in each quadrant after performing adjustment for casemix variables and provider characteristics. We will summarise the mean risk ratios for patients in each quadrant to identify

differences that may arise due to differences in casemix. We will repeat the analyses for the clinical specialties with the highest volumes across the three quadrants. Findings from this analysis will inform WP4 and WP5.

Coding practice

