NHS-funded hospital care (quadrants A and C in Diagram 1) is reimbursed through the national Payment by Results tariff system which incentivises detailed recording of comorbidities, but privately funded care in NHS private patient units (quadrant B) is reimbursed/charged according to the price schedules of insurers and hospitals. This may lead to differences in coding practice across sectors influencing comparisons of scope of practice (WP4) and performance (WP5). We will assess differences in the coding of comorbidities in terms of completeness and depth, across sectors and how coding changes over time. NHS funded patients in NHS hospitals vs independent hospitals offer an opportunity to compare coding in different providers but where the incentives for coding are the same. Similarly, comparing patients treated in NHS hospitals vs NHS private patient units offers an opportunity where the setting is the same but coding incentives and payments differ.

- Completeness: We will explore completeness of data fields, in terms of patient demographic characteristics (ie. age, gender, ethnicity, LSOA of residence) by quantifying the proportion of missing/unknown values for each demographic characteristic across the 3 quadrants and make comparisons between the quadrants over time.
- Depth: Diagnoses and procedures from HES are coded using International Classification of
 Diseases 10th revision (ICD-10) and OPCS-4 codes. Up to 20 diagnosis and 24 operation
 codes are recorded for each. Information in the first diagnosis position reflects the primary
 diagnosis, with subsequent positions documenting other comorbidities. Comorbidities will be
 extracted from all diagnosis and operation codes from hospital admissions between April
 2017 and February 2024. To compare coding depth, we will calculate the mean and
 standard deviation number of diagnoses codes for each patient, and calculated the mean
 number and standard deviation of diagnoses codes in each quadrant and make comparisons
 across age groups and over time.

WP2 – Survey of clinical governance leads in NHS and independent hospitals in England (RQ2, RQ3, RQ4 - lead [name])

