For each index admission we will calculate a set of quality and safety indicators, which have been validated for use with administrative data and are widely used for performance assessment in regulatory contexts (for example in monitoring against the NHS Outcome Framework, in CQC inspections/reviews, in clinical governance and appraisal/revalidation processes, etc) and for research purposes:

- 1) Unplanned readmission to hospital within 28 days of discharge (binary: yes/no),
- 2) Unplanned emergency department attendance within 28 days of discharge (binary: yes/no),
- 3) Emergency transfers to NHS hospitals at the end of the index admission episode (binary: ves/no).
- 4) Total length of continuous inpatient stay (accounting for transfers between hospitals) (continuous).
- 5) Death within 30 days of admission (binary: yes/no), and
- 6) Patient-reported health improvements within the first 6 months after surgery (for hip and knee replacement only) (continuous).

Each indicator will be summarised for index admission for quadrants A, B and C. Indicators 1-4 are constructed by linking index admissions to subsequent episodes of hospital care within Hospital Episode Statistics, which allows for such longitudinal follow-up through the use of a unique pseudonymised patient identifier (the Master Person Service ID). For indicator 2, we will additionally link admitted patient data to the Hospital Episode Statistics Emergency Care dataset, which captures all emergency department attendances in English hospitals from 2021.

Indicator 5 is constructed by linking Hospital Episode Statistics data to official Civil Registration data on date of death held by the Office for National Statistics. This linkage is performed by NHS Digital

based on the patient-identifiable data (e.g name, date of birth, NHS number) they hold. We will also consider an alternative outcome indicator based on in-hospital deaths as recorded in Hospital Episode Statistics (derived from the data fields discharge method & destination). This alternative approach captures mortality for the full patient population, including those that do not have an NHS number (e.g. patients not resident in England) or that for other reasons cannot be linked to Civil Registration data, but it necessarily fails to capture any deaths that occur after the end of the index hospital admission.

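### WP1 measures comorbidity coding depth only by the mean number of diagnosis codes per quadrant, which mixes how ill patients are with how fully illness is recorded

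*Protocol*

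**What the plan says.** The Coding practice subsection of WP1 states its aim as "We will assess differences in the coding of comorbidities in terms of completeness and depth", across sectors and over time. It then defines two measures.

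- **Completeness** is confined to demographic fields: "Completeness: We will explore completeness of data fields, in terms of patient demographic characteristics", measured as the proportion missing or unknown. It says nothing about comorbidities.
- **Depth** is the mean "number and standard deviation of diagnoses codes in each quadrant and make comparisons" "across age groups and over time". The first diagnosis position holds the primary "diagnosis, with subsequent positions documenting other comorbidities".

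Depth is therefore the only measure of comorbidity coding. Two contrasts are put forward to help interpret it. One is A against C, where payment incentives match: "NHS funded patients in NHS hospitals vs independent hospitals offer an opportunity to compare coding in different providers". The other is A against B, where the setting matches but the incentives differ.

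The Case-mix subsection of the same work package, using the same Hospital Episode Statistics data, lists as case-mix variables the "medical characteristics (length of stay, presence and count of comorbidities". In WP5 (Quantitative analysis of hospital data), the case-mix adjustment is to be specified from earlier published work and from what WP1 learns about data quality.

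**The concern.** Secondary diagnosis codes are read in two ways within one work package: as illness under Case-mix and as recording under Coding practice. A low mean in a quadrant could mean fitter patients, thinner recording, or both. The ambiguity also runs the other way, since deeper recording will look like heavier case mix.

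The coding assessment is there because the protocol expects coding differences to affect the WP4 and WP5 comparisons. If WP1 reports a coding difference that is really a morbidity difference, or misses a true one, the WP5 comorbidity adjustment will draw on a misleading input. That adjustment underlies the comparison of quality across quadrants and the hospital reports for case-study sites. Because the data are very large, any such difference would also be estimated with high apparent precision.

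**Working it through.** The protocol gives no figure for this analysis, so there is nothing to reproduce. The question is whether the planned quantity can separate recording from morbidity.

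**Model.** Let m be the true mean number of secondary conditions and r the proportion recorded. With one primary code per patient, expected codes = 1 + r × m. All values of m and r below are assumptions, because the documents give none.

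**Equal coding, different morbidity** (r = 0.8 in both; m = 2.0 and 1.2):
- First quadrant: 1 + 0.8 × 2.0 = 2.60
- Second quadrant: 1 + 0.8 × 1.2 = 1.96
- Ratio: 1.96 / 2.60 = 0.754, about 25% lower with identical coding

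Range: with m halfway between, (2.0 + 1.2) / 2 = 1.6, the second quadrant has 1 + 0.8 × 1.6 = 2.28, about 12% lower. With m = 2.0 in both, the difference is nil.

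**Different coding, hidden** (r = 0.6 with m = 2.0; r = 1.0 with m = 1.2):
- 1 + 0.6 × 2.0 = 2.2
- 1 + 1.0 × 1.2 = 2.2
- A 40-point recording gap shows as no difference.

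**Does splitting by age help?** Take three age bands with m = 1.5, 3 and 5 in a reference quadrant, and two comparison quadrants with the reference age mix:
- Morbidity 0.6 times the reference, r = 0.8: 0.6 × 0.8 = 0.48
- Reference morbidity, r = 0.48: 1 × 0.48 = 0.48

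Both have expected band means of 1 + 0.48 × 1.5 = 1.72, 1 + 0.48 × 3 = 2.44 and 1 + 0.48 × 5 = 3.40. A simulation of 400,000 patients per scenario, with overdispersed counts and a cap of 20 codes, gave 1.72/2.44/3.39 and 1.72/2.43/3.40. The standard deviations were 1.92 and 1.93, so reporting the SD does not separate the two cases either.

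**Can the ranking reverse?** Give the reference quadrant an age mix of 0.2/0.4/0.4 and r = 0.8. Give a quadrant with 0.6 times the morbidity an age mix of 0.3/0.4/0.3 and perfect recording:
- Reference: 1 + 0.8 × (0.2 × 1.5 + 0.4 × 3 + 0.4 × 5) = 1 + 0.8 × 3.5 = 3.80
- Fitter, perfectly coded: 1 + (0.3 × 0.9 + 0.4 × 1.8 + 0.3 × 3) = 2.89
- Fitter, standardised to the reference age mix: 1 + (0.2 × 0.9 + 0.4 × 1.8 + 0.4 × 3) = 3.10

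The better coder ranks lower even after age standardisation. Age stratification removes the problem only when the quadrants differ in age mix and in nothing else: in the simulation, 3.52 crude became 3.80 standardised.

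**The case against.** Several points on the other side are fair.

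- **Other elements give context.** The A–C and A–B contrasts hold the incentive or the setting fixed, trends within a quadrant are less exposed to stable differences between quadrants, and WP1 reports case mix and expected against actual mortality. These help interpretation. None holds morbidity fixed, however, and the mortality model adjusts for the same recorded variables. The Background also says the spread of patients across quadrants changes over time, so trends are not immune.
- **Downstream use is narrower than all admissions.** WP1 will pass on coding information for the procedures and specialties where the sectors overlap. That narrows morbidity differences but leaves selection within a procedure.
- **A within-patient measure is selective.** It rests on patients with repeat admissions, including transfers, and will be thin for quadrant B, which Diagram 1 puts at 0.6% of elective activity. This stands, and it is why the measure should be added alongside stratified full-population counts.

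Four stronger readings are tempting but unsupported.

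- A reader might infer that more codes will be reported as better coding. The protocol speaks only of depth.
- A reader might infer that patients in C are healthier. The protocol says only that unobserved characteristics may be unevenly distributed, and it gives no figures.
- A reader might infer that the WP1 result decides the WP5 adjustment. It is one input among several, with no decision rule. WP5 also adjusts for demographics, diagnosis and past healthcare use, and adds instrumental-variable models.
- A reader might put the illustrative gap at 40% (0.96 against 1.60). That leaves out the primary code, which the planned count includes.

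**Conclusion.** The point holds as a problem of identification. The one planned measure of comorbidity coding depends on the product of morbidity and recording, so followed as written it cannot attribute a difference between quadrants to coding. Age groups, calendar time and the two contrasts do not repair this.

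The size is unknown. The illustrative shortfall of about 25% with identical coding, and the fully hidden 40-point gap, rest on assumed rates. The shortfall shrinks to nothing if morbidity is equal across quadrants. The protocol itself fixes the measure, so this is more than a detail left open for later. A change should be made, because it is inexpensive and gives WP5 a more valid input.

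**What to change.** 1. Keep the mean and SD of diagnosis codes per quadrant, labelled as description.
2. Compare depth within strata of procedure, primary diagnosis, age and admission type.
3. Add a within-patient measure. WP5 already relies on "the use of a unique pseudonymised patient identifier (the Master Person Service ID" for follow-up. Among patients with admissions in two quadrants within 12 months, report the share of lifelong or chronic conditions coded at one admission that are coded again at the later one. Do this for A–C and C–A, and for A–B and B–A where numbers allow, with A–A pairs as reference.
4. Base statements about coding differences on items 2 and 3, and state that raw counts do not support such statements alone.

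If recording at the two admissions is independent, the expected share in item 3 equals r in the later quadrant, and m drops out. In the first example, A–A and A–C would both be 80%, correctly showing no gap. In the second they would be 60% and 100%, showing the gap that raw counts hide. Some conditions are always easier to code and reasons for admission differ, so the absolute share will not equal r exactly. The A–A reference is there for that reason.

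The cost is extra programming on linked data already planned, including a list of lifelong or chronic conditions. Stratification still leaves morbidity differences within strata. The within-patient measure describes only a selected group with repeat admissions, and pairs involving B will be few, so the A–B incentive question may remain imprecise.

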This is a mixed methods study, combining the use of a survey of clinical governance leads in NHS and independent hospitals; in-depth qualitative research in some case study "clusters" of linked NHS and independent hospitals; quantitative analysis of existing and newly available routine data sets on inpatient care; and qualitative work with patients with experience of both NHS and independent hospital care.

The development of this proposal has had close involvement and support from colleagues in a range of stakeholder organisations (the Independent Healthcare Provider Network, the Care Quality Commission, NHS Digital, the Private Healthcare Information Network, the General Medical Council, NHS England) and we attach several formal letters of support from these organisations and one from [name], formerly medical director of NHS England who previously chaired the DHSC review of cosmetic surgery and more recently chaired the group for IHPN which produced the Medical Practitioners Assurance Framework. Our Project Advisory Group will include representatives of all these organisations and others. We have also had extensive involvement from our PPI group. We have held two meetings with this group (consisting of five members) and have received written feedback from group members and lay reviewers at the NIHR Research Design Service. We have also consulted our PPI co-applicant throughout the design process.

We set out clear plans for the research to produce actionable research findings of real value to NHS organisations, independent healthcare providers, and the various stakeholder organisations outlined above in improving quality, safety and clinical governance, and for a programme of focused dissemination events and forums.

Background and rationale

We propose new research to help understand and improve the quality and safety of patient care in NHS and independent hospitals, through learning about the effectiveness and impact of shared arrangements for clinical governance. The funding and provision of acute hospital care in England is complex. Care may be publicly funded by the NHS or privately funded through health insurance or direct payment. Care may be delivered by NHS hospitals or by the independent sector. The diagram below illustrates the position.

Diagram 1. Funding and provision of elective acute inpatient care in England

Funding source

Care provision

	NHS	Private
NHS hospitals	A	В
	[88%]	[0.6%]
Independent	С	D
hospitals	[4.6%]	[5.8%]

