- Hospital Episode Statistics (NHS Digital): hospital data covering all NHS provided or NHS funded care. This includes private patients treated in NHS hospitals and NHS patients treated in independent hospitals (quadrants A, B and C from Diagram 1). Data cover patients admitted to hospital and A&E attendances. Data include information on patient characteristics; diagnosis and treatment codes; where the treatment is delivered; cost of treatment; the consultant responsible for each episode of care; length of stay; and how the patient was discharged. Data are of good quality, as they relate to how hospitals are funded for the care they deliver. We will use admitted patient data from 2014 to 2024 for WP1, WP4 and WP5 and A&E attendance data from 2021 to 2024 for WP5.
- Independent sector admitted patient care (PHIN): hospital data covering all admitted patient
 care that is privately funded (quadrants B and D from Diagram 1). The data items collected and
 data definitions are based on those in Hospital Episode Statistics for admitted patients. Note that
 no data are collected for privately funded outpatient care. The Competition and Markets
 Authority order mandates that all providers submit admitted patient data to PHIN. We will use
 aggregated data from 2017 to 2024 for WP1 and WP4.
- Patient-reported outcome measures (PROMs) for hip and knee surgery (NHS Digital): patient-level data collected using pre- and post-operative questionnaires completed by patients undergoing hip or knee replacement. All patients are invited to complete these questionnaires however their treatment is funded or provided. Patients report on changes in their health following surgery using validated condition-specific measures of self-reported health status (Oxford Hip Score and Oxford Knee Score). Aggregated PROMs data are available from PHIN

for privately funded treatment. NHS Digital will provide patient level PROMs data for NHS-funded treatment (quadrants A and C) and treatment in NHS private patient units (quadrant B). We will use data from 2022 to 2024 in WP5.

As providers of these datasets, NHS Digital and PHIN support the work and have been consulted in the planning of our research questions and work packages. PHIN have further been involved in developing the proposal. The research team has considerable experience in applying for and analysing hospital data and has long standing working relationships with NHS Digital.

Data storage

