Data from NHS Digital will be stored within an access restricted data share on the University's network storage infrastructure which is the recommended location for storing sensitive or critical University data. The storage infrastructure is hosted across two data centres for resilience and disaster recovery purposes. The data will be hosted on a strictly controlled data share within the University's network storage infrastructure to which only designated members of the research group staff will have access permissions. The data share will only be accessed via a mapped network drive initially on [name]'s PC for secure transfer (winscp) to the iCSF, and thereafter from the iCSF which has been identified for research data processing. The NHS Digital data will be accessed locally at the University of Manchester and via remote access to the University of Manchester system. Remote access will process NHS England Data in line with NHS England's remote access conditions. Data from PHIN will be stored only in PHIN's storage infrastructure and not in University of Manchester servers. Access to PHIN data will be via Virtual Desktop Infrastructure (VDI) technology to ensure the data is only processed within, and never leaves the PHIN virtual environment.

WP1 – Variations in hospital volume, case-mix and coding practice (RQ1, RQ4 - lead: [name])

Patient level data from Hospital Episode Statistics covered quadrants A, B and C. Aggregate data from PHIN covered quadrant D. These data will be analysed together to provide coverage of all four quadrants in Diagram 1. This combination will allow volume to be observed over a long time period covering both pre- and post-pandemic periods (2017 to 2024). Case-mix and coding practice will be analysed across quadrants A, B and C using Hospital Episode Statistics.

PHIN and Hospital Episode Statistics both contain information relating to quadrant B (private funding in NHS hospitals). Within Hospital Episode Statistics, activity from quadrant B can be identified using the fields relating to administrative category code and provider code. Within PHIN, identification is made using the provider code alone. Data from both sources will be compared to determine if volume is influenced by who collects the data. If differences are found, the most complete source of data will be used.

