Access to data from external providers will be negotiated with NHS Digital and PHIN and data processing agreements will be signed with both organisations. We will follow the information governance processes of the University Manchester to make sure that the data is transferred, stored, managed and analysed safely, and we will work closely with the UoM information governance team. Our team has extensive experience of analysing HES data as four members (TA,

CG, NG, KB) of the team have previously negotiated and obtained access to Hospital Episode Statistics from NHS Digital.

Volume

The annual volume of patients treated in each quadrant will be summarised from 2017 to 2024. Graphical and regression analysis will determine time trends over this period, seasonal effects, the impact of the COVID19 pandemic and how volume varies by geographical region and deprivation. Spatial maps will be used to identify areas with the greatest proportion of total care that is privately funded (quadrants B+D); and that is provided in an independent hospital (C+D). We will model how access to publicly-funded care, measured by NHS referral-to-treatment waiting times, varies with both private funding and care provision. To do so we will use waiting times data which are published each month for all NHS hospitals and furthermore broken down by treatment speciality. These waiting times will be matched to the volume of privately funded and provided care in the same speciality. This matching will first be done on hospitals closely located to each other, which assumes patients are less willing to travel for care, and then repeated for all providers regardless of location.

We will observe the procedures (and their clinical speciality) which are most commonly performed in each quadrant and identify the specialties/procedures with the greatest overlap across the NHS and independent sector. Together with our project advisory group, which includes our PPI co-applicant, we will select a set of procedures and specialties that will be the focus of our analyses for WP4 and WP5. The Competition and Markets Authority order, which mandates what data on privately funded care must be collected, does not cover outpatient care and such data are not collected by PHIN. Direct comparisons of volume between the NHS and independent sector will therefore only be made for procedures that are normally carried out as inpatient care.

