In Hospital Episode Statistics, each patient record includes the responsible consultant's General Medical Council number. PHIN also publish aggregated data for each consultant showing the volume of procedures performed and the independent providers they practice in. These PHIN aggregated data also include the General Medical Council number which means that it can be used to specify and aggregate the patient care provided by each individual consultant across NHS and independent hospitals. The General Medical Council number can also be linked with other sources of data (including the General Medical Council register) to derive other information about the consultant (such as their demographic characteristics, training, length of practice). Data like this have been used to describe and analyse the clinical workload, productivity, quality and safety of hospital consultants' practice in the NHS [27, 35] and evaluate the effect of changes to consultants' working lives such as the introduction of revalidation [36]. Until now, though, we have not been able to identify the scale and scope of consultant clinical practice across both NHS and independent sectors. Such analysis is crucial to monitoring and managing consultant performance and improving the quality and safety of patient care.

We will use the Hospital Episode Statistics and PHIN datasets to identify consultants who work across both the NHS and independent sectors in selected specialties (see WP1) and to describe their scale and scope of practice. For each consultant we will quantify the total number of patient episodes treated in each of the four funding/provision quadrants, and identify differences between consultants' practice in NHS and independent sector hospitals. Working at increasing levels of detail (from treatment specialty to procedure group to individual procedure codes) we will map consultants' activity, comparing their scope of practice in the NHS and independent sectors. In particular, we will highlight procedures which are carried out by consultants in independent hospitals (B+D) but rarely or not at all in NHS hospitals (A+C).

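### WP4's highlighting rule labels the funding columns of Diagram 1 (B+D and A+C) as hospital settings; by the protocol's own definitions independent hospitals are C+D and NHS hospitals are A+B

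*Protocol*

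**What the plan says.** The rule is in the Protocol, WP4 (scale and scope of consultant clinical practice). After planning to count each consultant's episodes by quadrant and to map activity down to procedure codes, it singles out procedures "carried out by consultants in independent hospitals (B+D) but rarely or not at all in NHS hospitals (A+C"). Two sentences earlier the same paragraph states the aim, which is to "identify differences between consultants' practice in NHS and independent sector hospitals".

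The letters are defined in Background and rationale ("Diagram 1. Funding and provision of elective acute inpatient care in England"). Columns are funding source and rows are care provision. The NHS-hospital row is A (NHS-funded) and B (private). The independent-hospital row is C (NHS-funded) and D (private).

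Other sections use the letters in the same way:

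- WP1, Volume: "greatest proportion of total care that is privately funded (quadrants B+D); and that is provided in an independent hospital (C+D").
- WP1, opening text: "quadrant B (private funding in NHS hospitals").
- WP1, Coding practice: "NHS-funded hospital care (quadrants A and C in Diagram 1").
- Patient datasets, Hospital Episode Statistics (HES): "This includes private patients treated in NHS hospitals and NHS patients treated in independent hospitals (quadrants A, B and C from Diagram 1").

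**The concern.** The WP4 sentence names two hospital settings but attaches to them the letter pairs for two funding sources. Both cannot be right, and an analyst who codes from the letters gets a different list from one who codes from the words.

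The rule is meant to pick out work that a consultant does in independent hospitals and seldom or never does in NHS hospitals. Under the letters, NHS-funded work in independent hospitals moves to the NHS side, and private work inside NHS hospitals moves to the independent side.

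Literal coding is a realistic risk. Patient datasets titles the PHIN source as independent-sector data but defines it as quadrants B and D. Anyone who treats PHIN records as independent-hospital records would reproduce the same grouping.

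**Working it through.** **1. What each letter pair means.**

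| Letters | WP4 calls it | Diagram 1 and WP1 make it | Share of elective inpatient care, 2020 (Diagram 1) |
|---|---|---|---|
| B+D | independent hospitals | privately funded | 0.6 + 5.8 = 6.4% |
| A+C | NHS hospitals | NHS-funded | 88 + 4.6 = 92.6% |
| C+D | (not used) | independent hospitals | 4.6 + 5.8 = 10.4% |
| A+B | (not used) | NHS hospitals | 88 + 0.6 = 88.6% |

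The four printed shares sum to 99.0%, not 100%. That does not affect anything below.

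**2. Which procedures change status.** Take one consultant and one procedure, and simplify *rarely or not at all* to *never*. Of the 15 possible patterns of presence across A to D, five are highlighted under at least one grouping:

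| Procedure done in | By the letters (in B or D, not in A or C) | By setting (in C or D, not in A or B) |
|---|---|---|
| D only | highlighted | highlighted |
| C only | no | highlighted |
| C and D | no | highlighted |
| B only | highlighted | no |
| B and D | highlighted | no |

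The two groupings agree on D only and disagree on the other four.

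**3. Putting *rarely* back.** The C-only and B-only results do not depend on the simplification, provided the volume is more than rare. The mixed patterns do depend on it. With a few C cases beside many D cases, A+C may still count as rare and the procedure would be highlighted. With a few B cases beside many D cases, the setting rule may highlight it too. So C-and-D procedures are missed only when C volume is more than rare, and B-and-D procedures are wrongly highlighted only when B volume is more than rare.

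**4. Illustration of the mechanism (an invented consultant).** Suppose 40 cases of a procedure, all in C. By the letters, B+D = 0 and A+C = 40, so there is no highlight. By setting, C+D = 40 and A+B = 0, so it is highlighted.

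**5. How much activity sits in the misplaced quadrants.**

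- C as a share of independent-hospital activity: C/(C+D) = 4.6/10.4 = 44%.
- B as a share of the activity WP4 labels independent: B/(B+D) = 0.6/6.4 = 9%.
- On the wrong side in total: B + C = 0.6 + 4.6 = 5.2 percentage points of elective inpatient care.

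**The case against.** Several things can fairly be said for the plan.

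*The letters may be what was meant.* B+D against A+C is a coherent private-versus-NHS-funded contrast, and the background section quotes a concern about private practice. This is possible but less likely. The paragraph states its aim by hospital setting, and RQ2 asks how organisations oversee the practice of doctors working in both kinds of hospital, and that oversight sits with the hospital. If funding was intended, the wording is wrong instead, and the sentence still has to change.

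*The paragraph partly protects itself.* Episode counts by separate quadrant do not depend on the faulty brackets, and a C-only procedure could still be seen in a procedure-level map kept by quadrant. This stands. It makes the error recoverable but does not make the rule right.

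*The effect is easily overstated.* A reader might infer three stronger things, none of which the protocol supports:

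- That the rule fails to find the practice it targets. It does not fail altogether: D-only procedures are highlighted under either grouping, and D (5.8%) is the larger independent-hospital quadrant.
- That 44% and 9% are error rates. They are national shares of all elective inpatient activity in 2020. WP4 covers cross-sector consultants in selected specialties, and the protocol says that the spread over quadrants varies by specialty, area and time. It gives no figure for how many consultant-procedure pairs would change status.
- That this highlight is the central RQ2 output and drives the consultant reports for case-study sites. RQ2 is wider than this one step. WP3 and WP4 promise selected reports and pilot profiles without saying that the highlight is in them. Measures of variation are left to a methodological review, and patterns of concern to clinical advisors.

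**Conclusion.** The rule is wrong as written. Its labels contradict Diagram 1 and every other use of the letters examined here. It is the one explicit highlighting rule in WP4, and read literally it can reverse the result for an individual consultant: C-only procedures are never highlighted, B-only procedures are highlighted wrongly, and mixed C-and-D or B-and-D procedures may go either way. D-only procedures are unaffected.

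The size can be stated only as activity: C is 44% of independent-hospital activity and B is 9% of the activity labelled independent, on 2020 national figures. The number of consultants affected cannot be derived from the protocol.

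The conclusion that setting is the intended contrast rests on the paragraph's stated aim and on RQ2. The conclusion that words and letters disagree needs no assumption. No test, estimate or sample size depends on the rule, but it should be corrected before WP4 is coded.

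**What to change.** In WP4, change the rule to procedures done in independent hospitals (C+D) but rarely or not at all in NHS hospitals (A+B). If a funding contrast is also of interest, report privately funded (B+D) versus NHS-funded (A+C) as a separate result under that label. It would also help to note in the analysis code that PHIN coverage (B and D) is not the same as independent-hospital care.

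The cost is one line of protocol and a regrouping in code. A, B and C come from HES and D from PHIN's consultant-level data. B can be separated by administrative category and provider code, and counts in all four quadrants are already planned, so no new data are needed.
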